8.2 Discontinuation of Individual Subject(s) From Study

All subjects who discontinue study treatment will remain in the study and must continue to be followed for protocol-specific follow-up procedures as outlined in the Schedule of Assessments [Table 1]. The subject will also be encouraged to attend all planned visits until the planned End of Study visit to provide data even if not on treatment anymore. The only exception to this is when the subject specifically withdraws consent/assent for any further contact with him/her or persons previously authorized by the subject to provide this information.

8.2.1 Lost to Follow-up

Every reasonable effort is to be made to contact any subject lost to follow-up during the course of the study to complete study-related assessments, record outstanding data and retrieve IP.

8.3 Discontinuation of the Study Site

If an investigator intends to discontinue participation in the study, the investigator must immediately inform the sponsor.

8.4 Discontinuation of the Study

The DSMB will review safety data periodically and provide a recommendation to the sponsor if the study should continue or be stopped due to safety concerns. The sponsor may terminate this study prematurely, either in its entirety or at any study site, for reasonable cause provided

Sponsor: APGD ISN/Protocol: 178-CL-204 EudraCT number 2016-001767-37

- CONFIDENTIAL -

that written notice is submitted in advance of the intended termination. Advance notice is not required if the study is stopped due to safety concerns. If the sponsor terminates the study for safety reasons, the sponsor will immediately notify the investigator and subsequently provide written instructions for study termination. The study may also be stopped as a result of the outcome of the interim analysis [Section 9.10 Interim Analysis and Early Discontinuation of the Study].

9 STATISTICAL METHODOLOGY

A statistical analysis plan (SAP) will be written to provide details of the analysis, along with specifications for tables, listings and figures to be produced. The SAP will be finalized before database hardlock. Changes from the planned analyses planned in the final SAP that impact the statistical analyses will be justified in the clinical study report (CSR).

In general, all data will be summarized with descriptive statistics frequency and percentage for categorical data. Data will be summarized by age group, treatment group and visit unless otherwise stated.

9.1 Sample Size

Efficacy of mirabegron in children will be based on both primary and secondary endpoints. Given the clinical hurdle to demonstrate efficacy in a population challenging to recruit, an alpha-level of 10% would appear reasonable and justified. In a study with propiverine in children, Marschall-Kehrel (2009) showed a difference in mean number of micturition episodes/24 hours of 0.8 between propiverine and placebo, with a SD between 2.2 and 2.3. Assuming at least similar efficacy of mirabegron, with a treatment effect of 0.9 micturitions per day between mirabegron and placebo and a common SD of 2.3, a sample size of 82 evaluable subjects (children) per treatment group is assumed per treatment group would provide a power of 80%.

These assumptions, together with levels for Type-1 error and power were agreed upon with Pediatric Committee in the current Pediatric Investigation Plan.

Under the assumption that after randomization about 10% of the subjects will not be evaluable for the analysis of the primary endpoint (i.e., not fulfilling the criteria for inclusion in full analysis set [FAS]), at least 184 children (5 to < 12 years of age) must be randomized in order to have at least 164 evaluable children for the analysis of the primary efficacy endpoint.

For adolescents, no formal sample size will be calculated; at least 32 adolescents (12 to < 18 years of age) must be randomized, yielding at least 16 adolescents on mirabegron. Further assuming a 50% screen failure rate, approximately 368 children have to be enrolled to achieve 184 children (5 to < 12 years of age) randomized and approximately 64 adolescents will be enrolled to achieve at least 32 adolescents (12 to < 18 years of age) randomized (at least 92 children and 16 adolescents must be randomized to mirabegron).

Recruitment will continue until the minimum number to be randomized in both children and adolescents have been achieved.

11 Feb 2021 Astellas Page 58 of 157

ISN/Protocol: 178-CL-204

9.2 **Analysis Sets**

Detailed criteria for analysis sets will be laid out in classification specifications and the allocation of subjects to analysis sets will be determined prior to database hardlock.

9.2.1 **Full Analysis Set**

The FAS will consist of all subjects who are randomized and receive at least 1 dose of IP and have at least 1 post baseline measurement for mean number of micturitions per 24 hours. The FAS will be analyzed by treatment arm as randomized (i.e., treatment arm based on randomization assignment). This will be the primary analysis set for efficacy analyses. Selected demographic and baseline characteristics will also be summarized for the FAS.

9.2.2 Per Protocol Set

The per protocol set (PPS) will consist of all subjects who are randomized and receive at least 1 dose of IP and have at least 1 post baseline measurement for mean number of micturitions per 24 hours, and who do not meet criteria for PPS exclusion. These criteria are to capture relevant nonadherence to the protocol and will be defined in the SAP. Further criteria may be defined in the SAP. The PPS will be a secondary analysis set for efficacy analyses.

Selected demographic and baseline characteristics may also be summarized for the PPS.

9.2.3 Safety Analysis Set

The safety analysis set (SAF) will consist of all subjects who took at least 1 dose of IP. The safety set will be analyzed by treatment arm as treated (i.e., based on the treatment the subject actually received rather than the treatment to which the subject was randomized). The SAF will be used for all summaries of demographic and baseline characteristics and all safety- and tolerability-related variables.

9.2.4 **Pharmacokinetics Analysis Set**

The pharmacokinetics analysis set (PKAS) will consist of all subjects who took at least 1 dose of IP for whom sufficient plasma concentration data are available to facilitate derivation of at least 1 pharmacokinetic parameter and for whom the time of dosing on the day before sampling. Additional subjects may be excluded from the PKAS at the discretion of the pharmacokineticist. Any formal definitions for exclusion of subjects or time points from the PKAS will be documented in the classification specifications and be determined at the classification meeting.

9.2.5 Pharmacodynamic Analysis Set

Not applicable.

9.3 **Demographics and Baseline Characteristics**

The summaries to be provided for demographics and baseline characteristics will be described here.

ISN/Protocol: 178-CL-204

9.3.1 Demographics

The demographic summary will include age, sex, race, ethnicity, body weight, height, body mass index (BMI) (at screening) and EBC. Baseline characteristics will include, among others, medical history, OAB diagnosis and history. Selected demographic and baseline characteristics will be summarized at least for the SAF and FAS.

Demographic data will be listed.

9.3.2 Subject Disposition

The number and percentage of subjects who completed and discontinued treatment and reasons for treatment discontinuation will be presented for all randomized subjects and for subjects in the SAF by age group, treatment group and overall. Similar tables for screening disposition, investigational period disposition and follow-up disposition will also be presented for all enrolled subjects by age group and overall. All disposition details and dates of first and last evaluations for each subject will be listed.

9.3.3 Previous and Concomitant Treatment (Medication and Nonmedication Therapy)

Previous and concomitant medications will be coded with WHO-Drug Dictionary (WHO-DD), and will be summarized by therapeutic subgroup (Anatomical Therapeutic Chemical [ATC] Classification System 2nd level), chemical subgroup (ATC 4th level) and preferred WHO name for the SAF. Subjects taking the same medication multiple times will be counted once per ATC level. A medication which can be classified into several chemical and/or therapeutic subgroups will be presented in all chemical and therapeutic subgroups.

A listing of previous and concomitant medications with ATC codes by WHO preferred name will be provided for all screened subjects.

9.3.4 Medical History

Medical history will be coded in MedDRA and will be summarized by SOC and preferred term (PT) for the SAF. Subjects will only be counted once per MedDRA level.

Medical history for each subject will be listed.

9.3.5 Investigational Product Exposure

Descriptive statistics for cumulative amount of the IP the subject was exposed to and average daily dose.

Duration of exposure will be summarized in the following by descriptive statistics.

Exposure time will be categorized according to the following categories for the treatment period:

- < 14 days
- At least 14 days, < 28 days
- At least 28 days, < 56 days
- At least 56 days

11 Feb 2021 Astellas Page 60 of 157

- CONFIDENTIAL -

Unknown

All IP exposure data will be listed.

9.4 Analysis of Efficacy

Efficacy analysis will be conducted on the FAS and PPS, and interpretation of results from statistical tests in children (5 to < 12 years of age) will be based on the FAS. The PPS will be used to assess the robustness of the results from the statistical tests based on the FAS. Efficacy analysis in adolescents will only be exploratory.

ISN/Protocol: 178-CL-204

9.4.1 Analysis of Primary Endpoint

9.4.1.1 Primary Analysis

The primary estimator for the primary estimand as defined in [Section 3.1 Estimand] will be calculated according to the evaluation of the primary efficacy endpoint. The primary efficacy endpoint change from baseline to week 12/EoT in mean micturitions per 24 hours (in children [5 to < 12 years of age]), will be analyzed using an analysis of covariance (ANCOVA). The ANCOVA model will include treatment group, sex and geographical region as fixed effects and the mean number of micturitions per 24 hours at baseline as covariate. This analysis will be performed and once with imputation of missing week 12 data using the last observation carried forward (LOCF) method.

The hypothesis for comparisons is given as follows:

H0: The adjusted mean change from baseline at week 12 in mean number of micturitions per 24 hours for mirabegron and placebo are the same.

H1: The adjusted mean change from baseline at week 12 in mean number of micturitions per 24 hours for mirabegron and placebo are not the same.

Statistical testing will be done at a 2-sided 0.1 significance level. A 90% CI for the treatment difference (mirabegron – placebo) will be provided. The primary analysis will use the FAS. The plausibility of the underlying assumption of missing at random for the primary estimator will be evaluated, and; therefore, the estimation of the treatment effect. Sensitivity analyses under alternative assumptions for missing data mechanisms such as missing not at random to show robustness of the estimates will be further specified in the SAP.

9.4.1.2 Secondary Analysis

The same analysis of the primary endpoint as described in [Section 9.4.1.1 Primary Analysis] will be conducted using the PPS, and without imputation using FAS.

The change from visit 3/week 0 (baseline) to visit 7/week 12 (EoT) in mean number of micturitions per 24 hours in children (5 to < 12 years of age) will be analyzed. The primary analysis for the primary endpoint will be using a repeated measures ANCOVA model with treatment group, visits (week 4, 8 and 12), sex, geographical region and the interaction between treatment group and visit as fixed effects and mean number of micturitions per 24 hours at baseline as covariate. Mirabegron will be compared to placebo using a linear

Sponsor: APGD ISN/Protocol: 178-CL-204

contrast within the repeated measures ANCOVA model, with 2-sided significance level of alpha = 0.1 and 90% CI. This analysis will be conducted using the FAS.

In addition to the parametric ANCOVA, a nonparametric ANCOVA will also be performed: (stratified) rank ANCOVA. This analysis will be conducted using the FAS.

9.4.1.3 Subgroup Analysis

For the primary efficacy endpoint, descriptive statistics (n, mean, 95% confidence interval around the mean, SD, minimum, median, maximum) will be calculated for mean change from baseline at each visit by sex, race, ethnicity, geographical region, formulation (tablets vs. oral suspension), prior OAB treatment and symptomatic UTI.

9.4.2 Analysis of Secondary Endpoints

The same analysis (ANCOVA) as for the primary endpoint will be applied to change from baseline at the end of the 12-week treatment period in children (5 to \leq 12 years of age) for:

- Mean volume voided per 24 hours
- Maximum volume voided
- Mean number of daytime incontinence episodes per 24 hours
- Mean number of nighttime incontinence episodes per 24 hours
- Mean number of daytime micturitions per 24 hours

Change from baseline in the number of dry (incontinence free) days per 7 days at the end of the 12-week treatment period will be analyzed with a negative binomial regression model including treatment group, sex, geographical region as factors and the log baseline rate of number of dry days (e.g., the log of the number of dry days divided by number of diary days at baseline) as covariate.

9.4.3 Analysis of Exploratory Endpoints

All efficacy endpoints for adolescents will be analyzed descriptively.

Data of the following explorative endpoints will be summarized, separately, for pediatric subjects:

- Percentage of subjects with a reduction in daytime incontinence episodes (< 50% reduction [nonresponder], 50% [partial responder] and 100% [responder])
- Improvement from baseline in worst incontinence grading
- Change from baseline at the end of the 12-week treatment period adjusted for fluid intake:
 - Mean number of micturitions per 24 hours
- Change from baseline at the end of the 12-week treatment period (adolescents only):
 - Mean number of micturitions per 24 hours
 - Mean number of daytime micturitions per 24 hours
 - Mean volume voided per 24 hours
 - Mean number of incontinence episodes per 24 hours

- CONFIDENTIAL -

• Number of dry (incontinence-free) days per 7 days at the end of the 12-week treatment period (adolescents only)

ISN/Protocol: 178-CL-204

Mean number of daytime grade 3 or 4 (Patient Perception of Intensity of Urgency Scale [PPIUS]) urgency episodes per 24 hours (adolescents only) will be summarized.

Correlations between the primary endpoint and mean volume voided, as well as incontinence episodes, will be explored.

Scatter plots will be presented to access the correlation between the primary end point, and mean volume voided and number of incontinence episodes at week 12.

9.5 Analysis of Safety

Safety analysis will be conducted on the SAF and conducted separately for children, adolescents and overall. Safety endpoints will be summarized using descriptive statistics.

9.5.1 Adverse Events

AEs will be coded using MedDRA. A TEAE is defined as an AE observed after starting administration of the IP and 30 days after the final administration of IP. An IP-related TEAE is defined as any TEAE with a causal relationship assessed as "yes" by the investigator.

The number and percentage of TEAEs, drug-related TEAEs, serious TEAEs, drug-related serious TEAEs, TEAEs leading to leading to withdrawal of treatment and drug-related TEAEs leading to leading to withdrawal of treatment will be summarized by SOC, preferred term, age group and treatment group. The number and percentage of TEAEs by severity will also be summarized. The worst severity will be summarized if the same AE is recorded more than once for a subject.

AE data will be listed.

9.5.2 Laboratory Assessments

For quantitative clinical laboratory measurements (hematology, biochemistry and urinalysis), descriptive statistics will be used to summarize results and change from baseline by treatment group and within treatment group and across age group.

Shifts relative to normal ranges from baseline to each visit during the treatment period in clinical laboratory tests will be tabulated.

Laboratory data will be listed.

The laboratory parameters that will be assessed during the conduct of the study are listed in [Appendix 12.7 Laboratory Assessments].

In cases where laboratory evaluations are conducted locally, the values obtained will be adjusted to values obtained by the central laboratory. Details will be described in the SAP.

9.5.3 Vital Signs

Descriptive statistics will be used to summarize vital sign results and changes from baseline by treatment group and within treatment group and across age group. For clinic

- CONFIDENTIAL -

ISN/Protocol: 178-CL-204

measurements Z-scores and percentiles for SBP and DBP will be calculated and summarized based on a comparison with age and height norms supplied by the Center for Disease Control and Prevention. Details to calculate Z-scores and percentiles will be provided in the SAP.

Z-scores and percentiles for pulse rate will be calculated and summarized based on a comparison with age norms based on Fleming [Fleming et al, 2011]. Details to calculate Z-scores and percentiles will be provided in the SAP.

Vital signs data will be listed.

9.5.4 **Physical Examination**

Abnormal findings/conditions identified during the physical examinations will be listed as part of the medical history for the screening visit, or as AEs at later visits.

9.5.5 Electrocardiogram

The routine 12-lead ECG results will be summarized separately for children (5 to < 12 years of age) and adolescents (12 to < 18 years of age) by treatment group and visit. ECGs will be recorded prior to blood draw.

9.5.6 Post Void Residual Volume

The PVR volume data and change from baseline data will be summarized by treatment group and within treatment group and across age.

9.5.7 **Acceptability and Palatability Questionnaire**

Results from the acceptability and palatability questionnaire for tablets [Appendix 12.8 Acceptability and Palatability Questionnaire for Tablets] and for oral suspension [Appendix 12.9 Acceptability and Palatability Questionnaire for Oral Suspension] will be summarized at week 12/EoT by age group and treatment group.

9.6 **Analysis of Pharmacokinetics**

Pharmacokinetic analysis will be conducted on the PKAS and conducted separately for children, adolescents and overall. Descriptive statistics (n, mean, SD, minimum, median, maximum, coefficient of variation (CV), geometric mean and geometric CV) will be used to summarize plasma concentrations of mirabegron by visit and time point. Further details will be specified in the SAP.

9.6.1 **Estimation of Pharmacokinetic Parameters**

The plasma concentrations will be analyzed with nonlinear mixed effects modeling (population pharmacokinetics) using Non-Linear Mixed Effects Modeling (NONMEM) software (version 7.3 or higher, ICON Development Solutions, [name], US) to estimate the pharmacokinetic parameters. Results will be reported separately.

9.7 **Analysis of Pharmacodynamics | Immunogenicity**

Not applicable.

ISN/Protocol: 178-CL-204

9.8 Other Analyses

Not applicable.

9.9 Major Protocol Deviations

Major protocol deviations as defined in [Section 10.3 Major Protocol Deviations] will be summarized for all randomized subjects by study site, treatment group and overall separately for children (5 to < 12 years of age) and adolescents (12 to < 18 years of age).

Major protocol deviation data will be listed by study site and subject.

The major protocol deviation criteria will be uniquely identified in the summary table and listing.

9.10 Interim Analysis (and Early Discontinuation of the Study)

A blinded interim analysis will be performed after 50% of children planned to be randomized have had their week 12/EoT assessment. The interim analysis will determine if the chance of a positive study with respect to the primary endpoint at the EoS is high enough to justify continuation of the study; otherwise, the study will be stopped for futility.

Given the data at the interim analysis, the independent data analysis center (IDAC) will calculate the predictive probability of a positive study. A positive study is defined as the final 1-sided p-value ≤ 0.05 when comparing Mirabegron vs. placebo in the primary efficacy analysis (in children [5 to \leq 12 years of age]). If the predictive probability is \leq 5% at this interim evaluation, the study will be recommended to stop for futility. Otherwise, the study will continue.

Detailed information on the decision rule of futility and simulations illustrating the operating characteristics of futility criterion will be presented in the SAP.

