6.3 Randomization and Blinding

6.3.1 Blinding Method

This is a double-blind study. Subjects will be randomized to receive mirabegron or placebo in a blinded manner such that neither the investigator, sponsor's study management team, clinical personnel, nor the subject will know which IP is being administered. The randomization number will be assigned based on information obtained from the interactive response technology (IRT) system.

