6.9 Interim Analysis (and Early Discontinuation of the Clinical Study)

One comparative interim analysis will be performed after 50% of children planned to be randomized have had their week 12/EoT assessment. Only data from those children with week 12/EoT assessment will be used in the interim analyses. The interim analysis will determine if the chance of a positive study with respect to the primary endpoint at the final analysis is high enough to justify continuation of the study; otherwise, the study will be stopped for futility.

Given the data at the interim analysis, a predictive probability of a positive study will be calculated. A positive study is defined as the final 1-sided p-value ≤ 0.05 when comparing mirabegron vs. placebo in the primary efficacy analysis (in children [5 to < 12 years of age]).

If the predictive probability is $\leq 5\%$ at this interim evaluation, the study will be recommended to stop for futility. Otherwise, the study will continue.

No efficacy analyses will be performed except for determination of futility.

At the interim analysis, the following predictive probability will be calculated: Predictive Probability of ({final one-sided p-value of mirabegron vs. placebo ≤ 0.05 } |Data).

Since we use non-informative prior distribution of difference in mean change from Baseline to week 12/EoT in mean number of micturitions per 24 hours between the mirabegron group and the placebo group and assume the mean change from Baseline to week 12/EoT in mean number of micturitions per 24 hours follows a Gaussian distribution, the Bayesian predictive probability for the event of a final one-sided p-value of mirabegron vs. placebo ≤ 0.05 (denoted by *PP*) can be obtained using a closed form based on the methods described in Geisser and Johnson (1994), Spiegelhalter etc. (2004), Dmitrienko and Wang (2006). Appendix 9.5 contains a detailed derivation.

$$PP = \Phi \left\{ \sqrt{\frac{2}{\frac{M_P}{N_P} + \frac{M_A}{N_A}}} \left[\sqrt{82} \frac{\overline{y}_{N_P} - \overline{x}_{N_A}}{\sqrt{2}\hat{\sigma}} - z_{0.95} \right] \right\}$$
(1)

where

- Φ stands for the cumulative distribution function for the standard Gaussian distribution. $\Phi(Z_{0.95}) = 0.95$.
- N_P and N_A denote the number of subjects observed at the interim analysis for placebo group and mirabegron group, respectively.

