- M_P and M_A denote the number of subjects as yet unobserved at the interim analysis for placebo group and mirabegron, respectively. $M_P = 82 - N_P$, $M_A = 82 - N_A$.
- \bar{y}_{N_P} and \bar{x}_{N_A} are the LS means for placebo group and mirabegron group, respectively, and will be obtained from the ANCOVA model described in Section 6.4.1.1.
- $\hat{\sigma}$ is the estimated pooled standard deviation and will be obtained from the same ANCOVA model as described in Section 6.4.1.1.

Detailed information on the decision rule for futility and simulations illustrating the operational characteristics of such futility criteria can be found in Appendix 9.4.

The interim analysis will be conducted by an Independent Data Analysis Center (IDAC). An independent statistician at this IDAC will be unblinded to conduct the interim analysis.

Documentation of the interim analysis will be kept at the IDAC until after end of study treatment unblinding, and will then be transferred to the Study TMF.

The recommendation from the IDAC (to stop the study for futility or continue as planned) will be forwarded to the Therapeutic Area Head Medical Specialties, to act upon this

recommendation (see Appendix 9.6: Interim Analysis Report Template). His decision to stop or continue the study will be communicated to the study manager.

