6.9.3 Report Generation

The IDAC will develop analysis programs based on surrogate treatment codes prior to the cut-off date. The unblinded IDAC statistician that is not affiliated with APGD will receive the unblinded randomization data from the IRT. The IDAC statistician will replace surrogate treatment codes with actual treatment codes and generate outputs using the programs developed by the IDAC.

The IDAC statistician will prepare a statistical report, being the Interim Analysis Report (Appendix 9.6) and the TFL (Table, figure and listing) outputs, see below, for the Therapeutical Area Head Medical Specialties.

Table Number	Table Title		
1.1	Disposition Prior to Randomization, All Subjects With Informed Consent		
1.2	1.2 Subject Classification, All Randomized Subjects		
1.3	Subject Enrollment, Overall and by Country/Site, All Randomized Subjects		
2	2 Demographics, Full Analysis Set		
3	Results of ANCOVA of Change from Baseline in Mean Number of		
	Micturitions per 24 hours at Week 12/EoT, Full Analysis Set		

For the interim report the following tables will be presented:

Note: no safety data will be presented

Table 10

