9.6 Interim Analysis Report Template

Study 178-CL-204 Interim Analysis Futility Analysis Results Generated by [IDAC Statistician's Full Name] on ddMMMyyyy

The performed Interim Analysis should determine if the chance of a positive study with respect to the primary endpoint at the final analysis is high enough to justify continuation of the study (Predictive Probability is ≥ 0.05); otherwise, the study should be stopped for futility.

Based on the following statistics calculated using the data by the cut-off date *ddMMMyyyy*:

- The number of subjects observed at the interim analysis for placebo and mirabegron group are *XX* and *XX*, respectively.
- The least squares means for placebo group and mirabegron group are *XX.X* and *XX.X*, respectively, for the mean change from baseline in mean number of micturitions per 24 hours at week12/EoT. The results are obtained from an ANCOVA model with treatment group, sex and geographical region as fixed effects and the mean number of micturitions per 24 hours at baseline as covariate. This analysis was performed with imputation of missing visit 7/week 12 data using the last observation carried forward (LOCF) method.
- The estimated pooled standard deviation is *XX.X*, obtained from the same ANCOVA model as described above.

Predictive Probability of ({final one-sided p-value of mirabegron vs. placebo ≤ 0.05 }|Data) = 0.XXX

Hence, the study [did or did not] meet the futility criteria "Predictive Probability is ≥ 0.05 ". The IDAC recommends the study to [continue or stop].

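### The protocol calls the futility interim blinded although its rule needs the between-arm difference, and the SAP contradicts itself on whether arm-level interim results leave the IDAC

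*Protocol*

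**What the plan says.** The protocol (version 2.0) uses the word blinded for the interim in the synopsis, in 4.1 and in 9.10: "A blinded interim analysis will be performed after 50% of children planned to be randomized have had their week 12/EoT assessment". Section 9.10 then says that "the independent data analysis center (IDAC) will calculate the predictive probability of a positive study", where positive means a final one-sided p-value of at most 0.05 for mirabegron against placebo. A predictive probability of 5% or less leads to a recommendation to stop. Protocol 6.3.1 defines the double blind: "neither the investigator, sponsor's study management team, clinical personnel, nor the subject will know which IP is being administered".

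The SAP (version 3.0) says in 6.9: "One comparative interim analysis will be performed after 50% of children planned to be randomized have had their week 12/EoT assessment". It adds: "An independent statistician at this IDAC will be unblinded to conduct the interim analysis". The IDAC's recommendation "will be forwarded to the Therapeutic Area Head Medical Specialties, to act upon this", with a pointer to Appendix 9.6, and that person's decision is passed to the study manager. The same section says that interim documentation remains with the IDAC until the study has been unblinded at its end.

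Section 6.9.3 goes further: "The IDAC statistician will prepare a statistical report, being the Interim Analysis Report", together with tables, and both are addressed to the Therapeutic Area Head. Table 3 in that list is the ANCOVA of the primary endpoint. The template in Appendix 9.6 has fields for the number observed in each arm, for the means ("The least squares means for placebo group and mirabegron group are", followed by blanks), for the pooled SD and for the predictive probability. Its closing line provides for either outcome, continue or stop.

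**The concern.** There are two separate faults.

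The first is one of wording. A rule that depends on how mirabegron compares with placebo cannot be applied to pooled, uncoded data. If blinded means that no treatment codes are used, the protocol's own rule cannot be run. If it means that only the IDAC sees the codes, the protocol does not say so, and SAP 6.9.3 with Appendix 9.6 departs from it by sending results by arm outside the IDAC.

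The second matters more. The SAP gives two incompatible instructions about what leaves the IDAC, and the more detailed one releases a midpoint estimate of the treatment effect while the trial may still be running. Several analysis choices are open after that point:

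- SAP section 1 allows revisions until database hard lock.
- Protocol 9.11 leaves pooling of geographical regions to a decision before hard lock, and region is a fixed effect in the primary model.
- SAP 4.5 and 4.5.1 leave per-protocol exclusions to a classification meeting before hard lock.
- SAP 6.10.3 leaves an outlier sensitivity analysis to judgment.

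If anyone with influence on these choices knows the interim effect, the sponsor cannot later show that they were made without it.

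**Working it through.** **1. Does the rule need treatment codes?**

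Inputs: N = 41 observed and M = 41 outstanding per arm (SAP Appendix 9.4); SD 2.3 and design difference 0.9 (protocol 9.1, SAP 3); one-sided 0.05, so z = 1.645; futility threshold 5% (protocol 9.10, SAP 6.9). Let Z be the interim statistic, positive when mirabegron is better, as in the SAP 6.9 formula.

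PP = Φ[(√(N+M)·Z − √N·1.645)/√M]. With N = M = 41 this is Φ(√2·Z − 1.645). PP ≤ 0.05 therefore means √2·Z ≤ 0, that is Z ≤ 0. The rule turns on the sign of the between-arm difference, which blinded pooled data cannot give.

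**2. Check against the SAP's own figures (Appendix 9.4, SD 2.3).**

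SE of the difference = 2.3 × √(2/41) = 0.508. For a true benefit of 0.9, Pr(futility) = Φ(−0.9/0.508) = Φ(−1.772) = 0.038; the SAP gives 0.038. Pr(success), from the bivariate normal of interim and final statistics with correlation √0.5, is 0.798; the SAP gives 0.797. With no true effect the results are 0.500 and 0.049; the SAP gives 0.501 and 0.050. The reading of the rule is therefore right, and one-sided type I error stays at or below 0.05.

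**3. What would the recipient learn?**

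From the full report: the LS means and hence the difference, with SE 0.51 at 41 per arm. If 50% is taken of the 184 to be randomized (92, or 46 per arm), SE = 2.3 × √(2/46) = 0.48.

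From the predictive probability alone, given arm sizes and SD (41 per arm, SD 2.3):

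| Observed benefit | Z | PP |
|---|---|---|
| 0.2 | 0.394 | 0.138 |
| 0.4 | 0.787 | 0.298 |
| 0.6 | 1.181 | 0.510 |
| 0.9 | 1.772 | 0.805 |
| 1.2 | 2.362 | 0.955 |

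The mapping is one-to-one, so removing the LS means but leaving the predictive probability would hide nothing.

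From a bare instruction to continue: only that the observed difference favours mirabegron (Z > 0). At 46 per arm, with M = 82 − 46 = 36, the boundary is Z = 1.645 × (√46 − √36)/√82 = 0.142, an observed benefit of 0.142 × 0.48 = 0.07.

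**4. The disclosure instructions side by side.**

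- SAP 6.9: records stay at the IDAC until after unblinding; the recommendation is what is forwarded.
- SAP 6.9, by its pointer to Appendix 9.6: the recommendation travels in a report that contains results by arm.
- SAP 6.9.3: that report and the tables, including the primary ANCOVA, are prepared for the Therapeutic Area Head.
- SAP 6.9.1: treatment codes are kept from sponsor staff. It says nothing about results.

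No sentence limits onward disclosure by the recipient. The first instruction cannot be followed together with the next two.

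**The case against.** The strongest reply is that the plan is sounder than it looks. Protocol 9.10 openly describes a mirabegron-versus-placebo calculation by an independent body, and 10.4.2 names the futility analysis as one of the IDAC's two purposes. Protocol 6.3.1 limits the blind to investigators, the study management team, clinical personnel and subjects. Read together, blinded can mean that the study team stays blinded. This stands: a reader might infer that ethics committees and sites were misled, and the documents do not support that. The adjective is wrong, but the calculation was disclosed.

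A reader might also infer that the plan clearly sends arm-level results to a sponsor executive. The documents stop short of this. The retention sentence in SAP 6.9 points the other way, so the fault is a contradiction. No text states who employs the Therapeutic Area Head; it is inferred from the title, the authority to stop the study, and the contrast with an IDAC statistician described as independent of the sponsor. That role may also fall outside the literal wording of 6.3.1.

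The harm should not be overdrawn. The role is given one action, the stop/continue decision. The estimate would be imprecise: at 41 per arm an observed 0.9 has a 90% interval of 0.9 ± 1.645 × 0.508, about 0.06 to 1.74. Nothing supports saying that half the trial remains to be run, because no accrual figures are given and later children may already be on treatment. Nor is there evidence that any change in SAP 3.0 was informed by interim data.

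Finally, SAP 3.0 mentions a possible protocol version 3, and the DSMB charter is separate. Either might resolve the matter, but neither can be checked here. None of this removes the conflict within the SAP.

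**Conclusion.** The point holds as two inconsistencies of unequal weight. The protocol's description of the interim as blinded does not fit its own rule or the SAP; alone, that is a minor wording correction. The SAP's conflict between 6.9 and 6.9.3 with Appendix 9.6 is worth settling before the interim, because one of the two readings releases the interim effect (SE about 0.48 to 0.51, design value 0.9) outside the IDAC while analysis choices remain open.

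A reader might infer that the false-positive rate is at risk. It is not: the interim can only stop for futility, and the one-sided error is 0.049 by calculation and 0.050 in the SAP's simulation. What is at risk is the ability to show that later choices were made without knowledge of the results.

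The conclusion rests on protocol 2.0 and SAP 3.0 as supplied, on SD 2.3, on 41 to 46 children per arm at the interim, and on the inference that the recipient holds a sponsor role.

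**What to change.** Protocol synopsis, 4.1 and 9.10: replace the word blinded with a description of an unblinded, comparative futility analysis carried out only by the IDAC, with the study team kept blinded.

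SAP 6.9.3 and Appendix 9.6: state that only the recommendation to continue or stop leaves the IDAC. Keep LS means, pooled SD, predictive probability and Table 3 at the IDAC (or with the DSMB) until database lock and unblinding, which is what the retention sentence in 6.9 already implies. The predictive probability must be withheld along with the means, because it maps directly to the effect.

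While the template is open, correct its futility criterion, which is printed as a predictive probability of at least 0.05, the reverse of protocol 9.10 and SAP 6.9.

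The cost is wording in three protocol places and a shorter report. The drawback is that the decision-maker acts on the recommendation alone. Little is lost, because the threshold is fully prespecified and applying it needs no judgment on arm-level figures.
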